3.2 Objectives

We hypothesise that existing cross-sectional imaging (MRE) from the routine NHS care of patients with CD can be used to screen patients for evidence of axSpA, thereby prompting onward referral to the rheumatology department for further management.

The objectives of this study are therefore to determine:

1. the validity, sensitivity, specificity and area under the ROC curve of MRE as a screening tool for axSpA in CD, using dedicated axial MRI scans with clinical assessment as the gold standard.
2. the proportion of patients with evidence of axSpA on MRE imaging who fulfill the 2009 ASAS criteria for axSpA, modified New York criteria for AS and the CASPAR criteria for PsA.
3. the proportion of these patients proceeding to non-pharmacological and pharmacological treatment of their axSpA, as a surrogate measure of change in clinical care as a result of MRE screening.
4. the extra-articular features associated with axSpA in CD, in order to better characterise the clinical phenotype of eSpA.
5. whether the site of CD (colon, ileum, etc.) predicts the occurrence of axSpA.

4. Study design

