4.3.2 Assessment of subjects with no lesions on MRE consistent with axSpA (controls)

Subjects (including those with a known diagnosis of SpA) who have consented to having their MRE scans reviewed, but who do not have lesions consistent with axSpA, will be informed in writing of this by the gastroenterology team. They will also be advised that they may be invited to enter the study as a control subject if they are randomly selected through matching (age and sex) to the enrolled 'MRE+ cases' (1:1 ratio). Matched potential control subjects will then be sent an invitation letter, PIS and reply slip (study interest form with a stamped-addressed envelope for returns) by the gastroenterology team to attend the rheumatology SpA research clinic to be assessed by [name] for clinical evidence of axSpA. CD subjects with a known diagnosis of SpA who are already under review by rheumatology and who have lesions on MRE consistent with axSpA will also be invited to attend this clinic for review outside of their routine NHS care but will be considered as cases. Informed consent for study participation in the SpA research clinic will be performed at the start of the consultation. The same clinical assessments, blood and stool samples and dedicated axial MRI scan of the spine and sacroiliac joints will be performed in this control group and in the group of CD subjects with a known diagnosis of SpA who are MRE+ as in the other cases, but will be funded by the research grant unless clinically indicated.

Control subjects in whom there is no evidence of axSpA (by ASAS, modified New York or CASPAR classification criteria) will be informed by letter, which will also be copied to the subjects GP and gastroenterology consultant. Control subjects who do have evidence of axSpA will be informed by letter (also copied to GP and gastroenterology consultant) and asked to return to [name] NHS rheumatology SpA clinic for ongoing care. CD subjects who already have a diagnosis of SpA (both in the control group and cases group) and are already under review by a rheumatology team will be informed by letter of the research clinic outcome and will be followed up as planned by their primary rheumatology team. We will also send a copy of the clinic letter to their GP, gastroenterology consultant and named rheumatology consultant to inform them of the clinic findings and to notify them of any outstanding tests/ management plans that may need to be considered at the next clinic review.

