8.1 Power analysis

This study will aim to include all CD cases with MRE imaging since 2015; the estimated sample size is therefore 1100 cases.

To our knowledge, there are no studies comparing the sensitivity and / or specificity of MRE scans with gold standard dedicated MRI for the detection of sacroiliitis. However, there have been some studies comparing CT imaging with MRI and these found MRI to be up to 17% more sensitive for the detection of sacroiliitis than CT [48, 49].

Although MRE is expected to be more sensitive at detecting evidence of sacroiliitis than CT, our power calculation is based on the conservative estimate that MRE will detect at $\geq 60\%$ (sensitivity) of

the cases of sacroiliitis, when compared with the gold standard dedicated axial MRI scan. Therefore with 80% power and a two-tailed alpha of 0.05, it is estimated that ≥ 60 control subjects (MRE normal) will be required for the study. It is estimated that a sample of >60 cases (with abnormal MRE scans) would be needed since the sample size required to assess specificity for a screening test is less than that of sensitivity. Case and controls will be recruited in a ratio of 1:1. From the 1100 MRE scans already performed, it is expected that $\geq 90\%$ will have a diagnosis of CD, i.e. 990 subjects. We estimate that $\geq 50\%$ of postally invited participants will consent to participate in the study, giving approximately 445 MRE scans for review.

The two previous studies assessing IBD patients for evidence of sacroiliitis using MRE imaging estimated the prevalence to be 16.7% and 15% [27, 28]. We therefore estimate to recruit ≥ 66 subjects with positive MRE scans (cases) and ≥ 66 matched controls. This is a conservative estimate, greater than the minimum number needed to recruit.

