8.2 Statistical analysis

Statistical input has been sought from the University of Cambridge Statistics Clinic (PhD student [name] and his supervisor [name]) and will be supported by [name]. Inter- and intra-rater reliability testing will be performed for the MRE and axial MRI assessments using intra-class correlation coefficients (ICC). The proportion of CD cases with evidence of axSpA on MRE imaging who fulfil diagnostic criteria for axSpA will be expressed as a percentage. Further descriptive analyses will also be performed on study participants. Due to the possible preponderance of patients with axial pain willing to participate in the study and therefore selection bias, we will not be able to calculate the true prevalence of axSpA in CD patients.

As it is expected that the majority of data collected will be count data with an excess of zero-values, a zero-inflated Poisson (ZIP) regression model will be used to test for association between the presence of axSpA, MRE score, PROMs, clinical indices, site of CD and blood biomarkers. In addition, ZIP regression will be used to test for association between MRE scores and those of dedicated axial MRI scans. Zero-inflated binomial regression will be used as appropriate, where the mean approximates the variance. Two-tailed tests will be performed, and the alpha set at 0.05.

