Appendix 4: List of sequences for the MRE protocol at Cambridge University Hospitals NHSFT

MRE Sequence	Fat Suppressed
2D CORONAL FIESTA	No
2D AXIAL FIESTA	No
2D CORONAL SLAB MRCP	No
CORONAL SSFSE	No
CORONAL SSFSE FS	Yes
CORONAL DWI B=600	No
CORONAL FIESTA MULTI Dynamic	No
CORONAL 3D LAVA FLEX GAD	Yes
AXIAL 3D LAVA FLEX GAD	Yes

Appendix 5: Assessment of spondyloarthritis international society (ASAS) criteria for classification of axial spondyloarthritis (to be applied in patients with chronic back pain and age at onset of back pain < 45 years) [50].

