Appendix 6: Modified New York Criteria for the diagnosis of ankylosing spondylitis [15].

Requires radiological criterion & ≥ 1 clinical criterion

Radiological criterion

Sacroiliitis grade ≥ 2 bilaterally or grade ≥ 3 unilaterally

Clinical criterion

1. Inflammatory low back pain & stiffness $\geq 30m$ that improves with exercise and is not relieved by rest
2. Reduced motion of the lumbar-spine in both sagittal & frontal planes
3. Limited chest expansion

(having excluded spinal fracture, intervertebral disc disease & fibromyalgia.)

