Appendix 7: Classification Criteria for Psoriatic Arthritis (CASPAR) [23].

To meet the CASPAR (CIAssification criteria for Psoriatic ARthritis) criteria, a patient must have inflammatory articular disease (joint, spine, or enthesal) plus ≥ 3 points from the following 5 categories:

1. Evidence of current psoriasis, a personal history of psoriasis, or a family history of psoriasis.

Current psoriasis is defined as psoriatic skin or scalp disease present today as judged by a rheumatologist or dermatologist.

† A personal history of psoriasis is defined as a history of psoriasis that may be obtained from a patient, family physician, dermatologist, rheumatologist, or other qualified health care provider.

A family history of psoriasis is defined as a history of psoriasis in a first- or second-degree relative according to patient report.

2. Typical psoriatic nail dystrophy including onycholysis, pitting, and hyperkeratosis observed on current physical examination.

3. A negative test result for the presence of rheumatoid factor by any method except latex but preferably by enzyme-linked immunosorbent assay or nephelometry, according to the local laboratory reference range.

4. Either current dactylitis, defined as swelling of an entire digit, or a history of dactylitis recorded by a rheumatologist.

5. Radiographic evidence of juxtaarticular new bone formation, appearing as ill-defined ossification near joint margins (but excluding osteophyte formation) on plain radiographs of the hand or foot.

(The CASPAR criteria have specificity of 98.7% and sensitivity of 91.4%)

(† Current psoriasis is assigned a score of 2; all other features are assigned a score of 1.)

Appendix 8: The spondyloarthritis research consortium of Canada (SPARCC): Magnetic Resonance Imaging index for scoring inflammation in the spine[43].

SCORING METHODOLOGY

1. All scores are dichotomous – present or absent.
2. After scanning the entire spine, 6 discovertebral levels are selected for scoring. These levels are chosen as representing the 6 most abnormal levels on the STIR sequence. Levels scored at a second time point are the same as those on the first.
3. After selecting levels, three consecutive sagittal slices are chosen for scoring at each level representing the most abnormal slices for that level.
4. Only abnormalities on the STIR sequence are scored. T1 SE images are included for anatomical reference.

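### Section 8.2 tests an undefined axSpA status against back-pain, mobility and psoriasis measures that help to define it, so those p-values are partly built in

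*Combined protocol and SAP*

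**What the plan says.** Section 8.2 plans zero-inflated Poisson regression to "test for association between the presence of axSpA, MRE score, PROMs, clinical indices, site of CD and blood biomarkers". These are hypothesis tests: "Two-tailed tests will be performed, and the alpha set at 0.05". The section does not define axSpA status for them, although it speaks of patients fulfilling diagnostic criteria.

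Status is described elsewhere in two ways. Section 4.3.1 assesses cases with ASAS, modified New York and CASPAR, and section 4.3.2 identifies controls with "no evidence of axSpA (by ASAS, modified New York or CASPAR classification criteria"). The aim (sections 1.2 and 3.1) instead names dedicated axial MRI together with clinical assessment, with no rule for combining the two.

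The criteria contain clinical features:
- ASAS (Appendix 5) is "to be applied in patients with chronic back pain and age at onset of back pain < 45 years".
- Modified New York (Appendix 6) needs the radiological criterion and at least one clinical criterion. The clinical criteria are inflammatory low back pain, limited chest expansion and "Reduced motion of the lumbar-spine in both sagittal & frontal planes".
- CASPAR (Appendix 7) needs inflammatory articular disease and at least 3 points. Its first category is "Evidence of current psoriasis, a personal history of psoriasis, or a family history of psoriasis"; current psoriasis scores 2, and nail dystrophy scores 1.

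The measures collected (sections 6.2 and 6.3) include VASbp, BASDAI, BASMI, and skin and nail psoriasis. Objective 4 seeks "the extra-articular features associated with axSpA in CD, in order to better characterise the clinical phenotype of eSpA".

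**The concern.** When a feature helps to decide who is called axSpA, a test of that feature between axSpA and the rest no longer has its nominal error rate. Someone classified by ASAS has chronic back pain by rule; 8.2 then asks whether back-pain scores are higher in that group.

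At stake is how the PROM and clinical-index results are read, and, for psoriasis, objective 4. Section 2.1 shows that the link between imaging change and symptoms is unsettled. One MRE study found no correlation between MRE score and inflammatory back pain, while two dedicated-MRI studies found such pain in most patients with sacroiliitis. A significant p-value against criteria-defined axSpA could be reported as evidence on this question when part of it comes from the classification rule.

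**Working it through.** The plan states no figure for this point, so there is none to reproduce. The check has three parts.

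**1. Criteria set beside tested measures**

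| Feature in the criteria | Where | Measure tested |
|---|---|---|
| Chronic or inflammatory back pain | Appendices 5 and 6 | VASbp, BASDAI (section 5.2.2.1 describes BASDAI as covering axial inflammatory pain) |
| Lumbar motion | Appendix 6 | BASMI |
| Psoriasis, nail dystrophy | Appendix 7 | Skin and nail psoriasis (6.3, objective 4) |

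The ASAS feature list is in a figure that is not available here, so no overlap is claimed for CRP or HLA-B27.

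**2. Size under a null**

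From the documents: two-sided alpha 0.05, and n = 66 + 66 = 132 (section 8.1: "We therefore estimate to recruit ≥ 66 subjects with positive MRE scans (cases) and ≥ 66 matched controls"). Everything else is assumed. Imaging change is made independent of symptoms, so a sound test should reject in about 5% of runs.

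*Rule A: MRI change alone qualifies, and a fraction q of back-pain patients without it also qualify clinically.* Assume MRI change in 40% and back pain in 40%.
- q = 0.1: P(axSpA) = 0.40 + 0.24 × 0.1 = 0.424. Back pain in axSpA = (0.16 + 0.024)/0.424 = 0.434; in the rest = 0.216/0.576 = 0.375.
- q = 0.2: P(axSpA) = 0.448. Back pain in axSpA = 0.208/0.448 = 0.464; in the rest = 0.192/0.552 = 0.348.
- Simulated Fisher-test rejection for presence of back pain: about 8% and 24%.
- For graded VASbp that is 1 SD higher in people with back pain, the built-in mean difference is only 0.434 − 0.375 = 0.06 SD or 0.464 − 0.348 = 0.12 SD. The SD within each group is about √(1 + 0.24) = 1.11. At q = 0.2 the groups are about 59 and 73, so SE = 1.11 × √(1/59 + 1/73) = 0.19, z = 0.116/0.194 = 0.60, and rejection is about 9%. At q = 0.1 (56 and 76), z = 0.30 and rejection is about 6%.

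*Rule B: back pain and sacroiliitis are both required.* Sacroiliitis in 20-60%, chronic back pain in 25-50%, Welch t-test, 2,000 runs per setting:

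| Test | Status by rule B | Status by MRI alone |
|---|---|---|
| VASbp, 1 SD higher with back pain | 39-95% | 4.6-6.0% |
| VASbp, 0.5 SD higher | 15-44% | not reported |

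With the 1 SD shift the built-in mean difference is 0.55-0.87 SD.

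*Mobility.* Status follows the modified New York structure: sacroiliitis plus back pain or reduced motion, with reduced motion taken as the worst 30% and MRI standing in for the radiological criterion. Rejection is 20-97%, against 4.7-6.2% with status by MRI alone.

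**3. CASPAR points**

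Patterns of the other four categories that reach 3 points:

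| Psoriasis category | All items available | Rheumatoid factor and hand or foot films unavailable |
|---|---|---|
| Current (2 points) | 15 of 16 | 3 of 4 |
| Personal or family history only (1) | 11 of 16 | 1 of 4 |
| None (0) | 5 of 16 | 0 of 4 |

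Rheumatoid factor and those films are not among the investigations listed in sections 4.3.1 and 6.4. Without them, nail dystrophy and dactylitis give at most 2 points, so some psoriasis item is needed. That item may be family history alone.

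**The case against.** **The definition is inferred.** Section 8.2 never says that axSpA means fulfilling the criteria. This stands, and is itself a gap. It does not remove the overlap, because the only other definition in the protocol, MRI with clinical assessment, also includes clinical features.

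**An analysis free of the overlap is already listed.** A reader might infer that the plan will find imaging disease linked to symptoms whatever the truth. The documents do not support that. The same sentence of 8.2 lists MRE score, which is an imaging measure read by assessors blinded to co-morbidities other than CD (section 4.2.1), and section 4.1 compares cases and controls defined by MRE alone. The overlap is confined to the tests against axSpA status.

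**The rates are assumed.** This stands: neither simulation uses the planned zero-inflated model, and the prevalences are not in the documents. A reader could also construct a rate near 100%, by testing presence of chronic back pain when axSpA requires both MRI change and back pain (100% against 0.24/0.84 = 29% in the rest). That tests the defining item itself under one assumed rule. VASbp, BASDAI and BASMI grade severity, and modified New York accepts any one of three clinical items, so the association is partly built in, not fully determined.

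**Psoriasis and objective 4.** It is tempting to say that everyone meeting CASPAR has psoriasis by construction. Appendix 7 does not support this: family history, nail dystrophy and dactylitis reach 3 points in a patient who never had it. Objective 4 concerns extra-articular features, so back pain and mobility lie outside it. Psoriasis is not named in 8.2 and enters through section 6.3 and objective 4.

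**Describing patients by accepted criteria is ordinary practice.** That is true of description. It does not justify p-values for the features that define the group.

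**Conclusion.** The point holds, at moderate severity. Tests of axSpA status against VASbp, BASDAI, BASMI and, through CASPAR, skin and nail psoriasis are biased towards an association, and nothing in the plan removes this. The inflation could be slight (about 6-9% for graded VASbp under rule A) or severe (up to 95% under rule B). The plan does not fix the rule or give the prevalences, so it cannot be pinned down further.

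A reader might infer that the study's main result is compromised. This overlap does not directly affect the sensitivity, specificity and AUC aim, MRE against axial MRI scores, MRE score against PROMs, or site of CD. The conclusion assumes that axSpA in 8.2 carries one of the two meanings given elsewhere in the protocol.

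**What to change.** In 8.2:
1. State how axSpA status is defined for the association tests, including how MRI and clinical assessment combine.
2. For features that appear in Appendices 5-7, report comparisons by criteria-defined axSpA descriptively, without p-values.
3. Test those features against the consensus dedicated-MRI scores (SPARCC and the custom score) in subjects who had the scan. Use them as scores, or with a cut-off fixed before analysis.

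The cost is small, because section 4.3.3 already plans these scores for cases and controls. Three limits should be acknowledged. The protocol gives no MRI positivity cut-off, so one chosen after seeing the data would be data-driven; using the scores directly avoids this. Section 6.7 lets subjects decline the scan, so the number scanned should be reported. The target also changes: these tests concern correlates of imaging disease, including symptom-free disease, rather than of clinical axSpA, and the report must say so.

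### The Assess sample is half MRE-positive by design and section 8.2 does not account for this, so results for objectives 4 and 5 would mainly describe MRE-visible axSpA

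*Combined protocol and SAP*

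**What the plan says.** Sections 4.3.2 and 5.2.2.2 draw controls at random from MRE-negative patients, matched on age and sex to the enrolled MRE-positive cases. Section 4.3.2 gives both groups the same clinical assessment and dedicated MRI, so axSpA can be found in either. Section 8.1 fixes the mix: "Case and controls will be recruited in a ratio of 1:1". It sets the expected size: "We therefore estimate to recruit ≥ 66 subjects with positive MRE scans (cases) and ≥ 66 matched controls". The expected rate of positive scans comes from two earlier MRE studies, which "estimated the prevalence to be 16.7% and 15% [27, 28".

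Section 8.2 uses a zero-inflated Poisson model to "test for association between the presence of axSpA, MRE score, PROMs, clinical indices, site of CD and blood biomarkers". It mentions neither sampling weights, nor stratification by MRE result, nor the matching. MRE score is in the list of variables, but its role is not stated. The one selection effect that 8.2 names is volunteering by patients with axial pain, and it uses this only to rule out a prevalence estimate.

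In section 3.2, objective 4 is "the extra-articular features associated with axSpA in CD, in order to better characterise the clinical phenotype of eSpA". Objective 5 asks whether the site of Crohn's disease predicts axSpA. Neither is limited to MRE-positive patients.

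**The concern.** Whether a patient has axSpA is established in the Assess phase, and entry to that phase depends on the MRE result. A group that is about one sixth of the screened patients becomes half of those analysed. The axSpA patients in the sample are therefore weighted heavily towards those whose disease shows on MRE, and those whom MRE misses are thinned out.

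If a feature or a disease site is more or less common in MRE-visible than in MRE-missed axSpA, its frequency and its association with axSpA in the pooled sample will differ from those in the screened cohort. A screening study has particular reason to describe the patients whom the screen misses. This point concerns objectives 4 and 5. The accuracy estimates under objective 1 are a separate matter and are not treated here.

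**Working it through.** **Inputs**
- m, the MRE-positive rate in the cohort: 15% or 16.7% (8.1).
- s, the MRE sensitivity: 60% (8.1). This is a planning minimum for sacroiliitis against dedicated MRI. Using it for axSpA is an assumption, so it is varied below.
- Sample: 66 MRE-positive and 66 MRE-negative, 1:1 (8.1).
- PPV, the share of MRE-positive patients who have axSpA: not given. Assumed 20% to 100%.

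**1. The plan's figure.** 445 × 0.15 = 66.75, so at least 66 cases is reproduced. The 445 does not follow from the stated steps, since 1100 × 0.90 × 0.50 = 495; it appears if the 90% is applied twice (445.5). The shares in step 2 do not use it.

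**2. Share of axSpA patients who are MRE-positive.** In the cohort the odds are s/(1 − s). With equal numbers from each MRE group, an MRE-positive patient is (1 − m)/m times as likely to be in the sample as an MRE-negative one. So:

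sample odds = s/(1 − s) × (1 − m)/m

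- m = 15%, s = 60%: 1.5 × 5.67 = 8.5, a share of 8.5/9.5 = 89.5%.
- m = 16.7%, s = 60%: 1.5 × 4.99 = 7.48, a share of 7.48/8.48 = 88.2%.

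| Sensitivity = cohort share | Sample share, m = 15% | Sample share, m = 16.7% |
|---|---|---|
| 50% | 85.0% | 83.3% |
| 60% | 89.5% | 88.2% |
| 70% | 93.0% | 92.1% |
| 80% | 95.8% | 95.2% |

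PPV does not enter the formula, so these shares do not depend on it.

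**3. Expected numbers.** MRE-negative axSpA among 66 controls = 66 × PPV × m/(1 − m) × (1 − s)/s. At m = 15% and s = 60% this is 66 × PPV × 0.1765 × 0.6667 = 7.76 × PPV.

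| Assumed PPV | MRE-positive axSpA | MRE-negative axSpA |
|---|---|---|
| 20% | 13.2 | 1.6 |
| 60% | 39.6 | 4.7 |
| 100% | 66 | 7.8 |

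At m = 16.7% the last column runs from 1.8 to 8.8.

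**4. Illustration of bias (all feature rates assumed; m = 15%, s = 60%).**
- Feature in 50% of MRE-positive and 20% of MRE-negative axSpA: cohort 0.6 × 0.50 + 0.4 × 0.20 = 38%; sample 0.895 × 0.50 + 0.105 × 0.20 = 46.8%. If 10% of patients without axSpA have it whatever their MRE result, the odds ratio is (0.38/0.62)/(0.10/0.90) = 5.5 in the cohort and (0.468/0.532)/(0.10/0.90) = 7.9 in the sample.
- Feature in 30% and 60%: cohort 42%, sample 33%. The bias can run either way.
- Feature in 40% of both: 40% in cohort and sample. No bias.

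**5. Effect of weighting (m = 15%, s = 60%, PPV 100%).** Giving each control the weight 5.67 relative to a case returns 66/(66 + 7.76 × 5.67) = 66/110 = 60%. The effective number of axSpA patients is 110²/(66 + 7.76 × 5.67²) = about 38, against 66 + 7.76 = about 74 unweighted.

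**The case against.** **A reader might infer that objective 4 would describe MRE-visible disease only.** The documents do not support that. Controls are a random matched draw with the same assessments, so some MRE-missed axSpA will be found: about 10% to 12% of the axSpA group at 60% sensitivity.

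**A reader might take 90% against 60% as the expected result.** The 60% is a conservative minimum for sacroiliitis, whereas the reference standard for axSpA is MRI with clinical assessment. At 80% sensitivity the gap narrows to about 96% against 80%.

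**A reader might say that 8.2 plans a wrong analysis.** It does not say how the two groups are combined. Section 4.1 speaks of comparing them, and MRE score is a listed variable. Conditioning on the MRE result would deal with much of the sampling, but it answers a question within MRE groups. The supportable defect is that 8.2 leaves this unspecified.

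**The link to objective 4 is indirect.** The sentence in 8.2 names no extra-articular features. It reaches objective 4 through clinical indices and the descriptive analyses. It reaches objective 5 directly, because site of disease is in the list.

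**The harm may be small beside the noise.** In the first illustration, with PPV assumed at 75%, there would be about 55 axSpA and 77 other patients. The 95% interval around 7.9 is then roughly 3.2 to 20 and covers 5.5. That stands as a caution on size, but imprecision does not remove a systematic shift.

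**Weighting is fragile.** A handful of patients would carry about 40% of the axSpA weight, age-sex strata would be sparse, and weights restore only the mix among those who consented to screening. This stands, and it is why weighting belongs in a sensitivity analysis.

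**Conclusion.** The point holds as a gap in the analysis plan for objectives 4 and 5. The sample is selected on the MRE result, and 8.2 does not say how that selection is handled. If sensitivity for axSpA is 60% and 15% to 16.7% of screened patients are MRE-positive, about 88% to 90% of sampled axSpA patients would be MRE-positive, against 60% in the cohort. The results would then be predominantly, not only, about MRE-visible axSpA.

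The calculation assumes that taking part in the Assess phase is unrelated to axSpA within each MRE group, and it ignores the age-sex matching. Bias in a given result further requires that the feature be related to MRE result within axSpA status. The documents give no data on this, so neither the size nor the direction of bias can be stated.

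**What to change.** In section 8.2:

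1. Report axSpA features and site of Crohn's disease separately for MRE-positive and MRE-negative subjects.
2. State that pooled frequencies and associations come from a sample enriched for MRE-positive patients.
3. Word the conclusions for objectives 4 and 5 as mainly about MRE-visible axSpA, unless enough MRE-negative axSpA is found to say more.
4. As a sensitivity analysis, weight each subject by the inverse of the actual sampling and participation fractions in both MRE groups, by age-sex stratum where numbers allow, with robust standard errors. Use observed fractions, not planned ones, because the Assess phase has its own consent step (5.2.2.2) and not every MRE-positive patient will enrol.

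The cost is a few sentences, one table and one further analysis on data already to be collected. The drawback is wide intervals for the MRE-negative group and for the weighted results, since only about 2 to 8 MRE-negative axSpA patients are expected (15% MRE-positive, 60% sensitivity, assumed PPV of 20% to 100%).
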